1.0 Aims

The goal of this study is to determine the extent to which standard care plus the Anticoagulation Choice tool promotes shared decision making (SDM) and impacts anticoagulation uptake and adherence versus standard care without this tool in patients with nonvalvular atrial fibrillation (AF).

Aim 1. To what extent does use of the ANTICOAGULATION CHOICE tool promote high-quality SDM versus standard care?

Using encounter video recordings and post-visit patient and clinician questionnaires, we will assess **SDM quality** (primary endpoint) **and processes**.

We hypothesize that use of the tool will improve SDM irrespective of patient literacy/numeracy, stroke risk, anticoagulation use at baseline, or type of clinic.

Aim 2. To describe the impact Anticoagulation Choice tool has on the rate of anticoagulation, the choice of anticoagulant, and adherence to anticoagulation in at-risk patients with AF versus the impact of standard care.

Using medical records and pharmacy profiles, we will determine the choice of anticoagulation, changes in anticoagulant use over time, and 12-month drug persistence, in all patients and in subgroups defined by patient literacy/numeracy, stroke risk, anticoagulation use at baseline, and type of clinic. As safety outcomes, we will monitor serious bleeding or strokes requiring medical attention.

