Data to be collected on patients include variables necessary to estimate the risk of stroke and bleeding, age, gender, BMI, smoking status, alcohol consumption, marital status, annual income of household, highest level of education, residency (nursing home), location of primary healthcare and total number of medications patients is currently taking. To further characterize the patients, we will use Chew et al single-item health literacy screener,⁴⁶ a 4-item modified Subjective Numeracy Scale,^{47, 48} and a single-item health status measure.⁴⁹

We will collect information on past use of anticoagulants through medical record review. We will categorize the patients into two cohorts for descriptive and analytical purposes. For patients who are not using an anticoagulant at the time of trial participation will form the 'Start' cohort. They may have used anticoagulation and discontinued >6 months ago, never used anticoagulation, or are using aspirin only. Patients that began an anticoagulant

within the past 10 days of the enrolled encounter that were prescribed an anticoagulant within the emergency department or an inpatient visit will still be considered a new ‘Start’.

Patients who are on warfarin or NOACs or used them in the past 6 months will form the ‘Review’ cohort. This cohort may include patients who have difficulty maintaining a therapeutic INR, or patients considering switching to a different anticoagulant or to stay on warfarin but switch to home INR monitoring.

The post consent survey for clinicians will collect demographic data (age, gender, specialty, % of their practice dedicated to anticoagulation care).

Calendar of Events

	Prior to Study Enrollment	Prior to Encounter		Post Encounter	12 months Post Enrollment
Patient Completed Forms			R A N D O M I Z E D A T I O N		
Informed Consent	X				
Pharmacy Consent	X				
Survey				X	
Phone ¹					X
Clinician Completed Forms					
Informed Consent	X				
Survey		X		X	
Clinical Data Abstracted from EMR					
Bleeds					X
Strokes					X
INR Tests (# and values outside of 2-3 range)					X
Anticoagulation Prescription		X		X	X
Pharmacist Request					
Anticoagulation					X ²

Use					
-----	--	--	--	--	--

- 1- Patients who do not have utilization within enrolling healthcare system will be contacted via phone for verification of safety data (strokes and bleeds). If no information in the record and follow-up is necessary we will call patients the maximum number allowed by the IRB followed by a postal survey

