4.9 Statistical Analysis

4.9.1 Analysis Plan

The study will be analyzed according to the *intention to treat principle (ITT)*, including all patients enrolled to the study in the arm to which they were assigned, regardless of which they were assigned to (e.g., standard care or Anticoagulation Choice + Standard Care). Reporting will include 'Per Protocol', complete data for each arm plus the ITT analysis where imputation analysis methods will be utilized to address any missing values (see section 4.9.1.1 for details on missing data analysis). Baseline characteristics will be reported in the study results with continuous values being reported as means and standard deviations and categorical values reported as counts and frequencies and compared between study arms using t-tests and chi-squared tests. Any baseline imbalances ($p < 0.05$) will be explored as a possible factor to adjust for when the outcome measures are

analyzed. We will adhere to the CONSORT guidelines to transparently report study results and ensure that sufficient information is included to allow for assessment of the study's internal and external validity.

We will use standard techniques appropriate for trials, with each outcome compared between study arms using t-tests for continuous outcomes and chi-square tests for dichotomous outcomes. If there are differences in baseline characteristics found by statistical means or found to have clinical relevance between the two study groups, these will be accounted for using regression models which include an indicator for study arm.

We will perform descriptive analyses to describe any potential heterogeneity of treatment effect (HTE) and facilitate synthesis of subgroup results in future meta-analyses. We will conduct descriptive HTE analyses by clinic (academic, community and safety net), by cohort (start or review cohort), by stroke risk (CHA₂DS₂-VASc score of 1 or ≥ 2 for men and 2 or ≥ 3 for women), and by numeracy (Less than adequate vs. not). The outcomes assessed with HTE analyses will be the same as those assessed in the trial (e.g., SDM and communication quality, knowledge, and decisional satisfaction).

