4.9.2 Sample Size Estimation

*The table shows the detectable effect for each of the outcomes of interest if we were to have data on that outcome from a total of 333 patients (1% of available population). This provides enough power ($\alpha=0.05$; two-sided difference) to detect meaningful differences across arms for all SDM quality and process outcomes. Our intent, however, is to have enough power to detect important differences when we conduct analyses of groups or cohorts of patients. Most of these analyses will divide the participants into 2 cohorts (e.g., start and review cohorts), except for the subgroup analysis by clinic, which divides the total sample into 3 cohorts: academic, community, and safety net clinic. That is the only analysis with three groups. Given this, we would need 3 times the sample size listed in the table, or **999 participants (3% of available sample)** to address all planned subgroup analyses. These are minimum targets for recruitment and we do not plan to limit recruitment in any way to enroll up*

to this number of patients. It assumes even distribution of participants per subgroup (e.g., start vs. review cohort); since the only grouping with three levels is clinic, each clinic will be expected to recruit similar numbers. Thus, for the main analysis and for other subgroup analyses (n=2 levels),

Outcome (n = 333)	Rate (%) or SD	Detectable effect	Power*
Patient level – SDM quality			
Knowledge transfer [^]	18	5.6	84%
Knowledge of risk	55%	15%	81%
Decisional conflict scale [^]	17	5.2	80%
Clinician level			
Satisfaction [^]	54%	15%	80%
Encounter level – SDM process			
Engagement (OPTION12) [^]	12.6	3.9	80%

[^] Values from iADAPT SDM tool trial; * $\alpha=0.05$; two-sided

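### Aim 1 claims benefit irrespective of subgroup, but the plan specifies no arm-by-subgroup contrast and leaves literacy off the subgroup list

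*Combined protocol and SAP*

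**What the plan says.** Section 1.0, Aim 1: "We hypothesize that use of the tool will improve SDM irrespective of patient literacy/numeracy, stroke risk, anticoagulation use at baseline, or type of clinic". The second aim names the same factors, literacy/numeracy included, as subgroups for the anticoagulation outcomes.

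Section 4.9.1 describes the subgroup work as descriptive: "We will perform descriptive analyses to describe any potential heterogeneity of treatment effect". It gives two purposes, describing heterogeneity and helping later meta-analyses. The factors are clinic type ("We will conduct descriptive HTE analyses by clinic (academic, community and safety net"), cohort (start or review), stroke risk, and finally numeracy: "and by numeracy (Less than adequate vs. not". Literacy is not listed, although section 4.6 collects it with a "single-item health literacy screener". The hierarchical models in 4.9.1 cover clinician-level correlation and covariate adjustment. No interaction term, heterogeneity test or consistency criterion appears anywhere.

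Section 4.9.2 tabulates detectable differences between arms "if we were to have data on that outcome from a total of 333 patients" and calls that number sufficient for all quality and process outcomes. It then adds: "Our intent, however, is to have enough power to detect important differences when we conduct analyses of groups or cohorts of patients". Because clinic type has three levels, 333 is multiplied by three to give 999. For persistence, the same section sets a separate subgroup calculation: 100 per arm, one-sided alpha 0.05, 80% power for 16 percentage points.

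**The concern.** A hypothesis that the tool helps irrespective of several patient and clinic factors needs an analysis that compares the effect across levels of those factors. The plan has none. What it does have is a sample size in which two thirds of recruitment (666 of 999) is justified by detecting an arm difference inside each clinic type. That makes it easy to judge consistency by asking in which subgroups the difference reached significance, and such a tally does not show whether effects differ. Chance alone will often make some subgroups significant and others not when the true effect is the same in all.

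For literacy the gap is simpler. It is part of the hypothesis and is measured, yet the heterogeneity list gives it no analysis. As written, part of Aim 1 would go unanswered.

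**Working it through.** **Inputs (section 4.9.2).** 333 patients per comparison, two-sided alpha 0.05. Decisional conflict: SD 17, effect 5.2, stated power 80%. Knowledge transfer: SD 18, effect 5.6. Subgroups evenly sized. Assumed: 1:1 allocation (the ratio is not stated), no clinician clustering, no missing data.

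**1. Reproduce the plan's figure.** With 166.5 per arm, SE = 17 × √(2/166.5) = 1.863. Power = Φ(5.2/1.863 − 1.96) = Φ(0.831) = 79.7%, against the stated 80%. The rows for knowledge of risk, clinician satisfaction and OPTION12 also reproduce to within a point. Knowledge transfer gives 81.0% against a stated 84%.

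**2. Mixed significance under a uniform effect, three clinic types.** With power p in each of k independent subgroups, the chance of some significant and some non-significant results is 1 − p^k − (1 − p)^k.
- At p = 0.80, k = 3: 1 − 0.512 − 0.008 = 48.0%.
- At p = 0.797 (decisional conflict): 1 − 0.506 − 0.008 = 48.5%.
- Across all the tabulated outcomes: 46% to 49%.

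**3. Sensitivity to the true effect (decisional conflict, clinic type).**
- 0.75 times (3.9 points): p = 55.3%, mixed 74%.
- 1.25 times (6.5 points): p = 93.7%, mixed 18%.
- 1.5 times (7.8 points): p = 98.7%, mixed 4%.
- Planned effect, but clinic groups of 50/30/20%: mixed 57% to 59% across the continuous outcomes.

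**4. Two-level factors.** Even split, 499.5 patients per level: SE = 17 × √(2/249.75) = 1.521; p = Φ(5.2/1.521 − 1.96) = 92.8%; mixed = 2 × 0.928 × 0.072 = 13%. A 20/80 split gives 41% to 42% across the continuous outcomes.

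**5. All four listed factors together.** A simulation of 4,000 trials of 999 patients, with the planned decisional-conflict effect uniform throughout, gave mixed significance on at least one factor in 53%. A heterogeneity test on the same data wrongly flagged each factor 4.9% to 5.3% of the time, and at least one of the four 19% of the time.

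**6. What an interaction analysis can detect at 999.** Evenly split two-level factor: interaction SE = √2 × 1.521 = 2.151. The difference detectable with 80% power is (1.960 + 0.842) × 2.151 = 6.0 points. For knowledge transfer the SE is 2.278 and the difference 6.4 points. Both exceed the table's main effects of 5.2 and 5.6. If subgroup effects differed by the whole planned effect, power would be 68% for decisional conflict and 69% for knowledge. For clinic type, with the planned effect in two types and none in the third, the 2-df test has 52% to 53% power.

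**The case against.** The strongest reply is that the plan never says consistency will be judged by significance within subgroups. It calls the analyses descriptive, which fits reporting subgroup estimates with intervals. That stands. A reader might infer a testing rule from 4.9.2, which gives subgroup comparisons their own power and alpha, but the documents do not state one. The defect is that the contrast is unspecified; no wrong method is prescribed.

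Three further points have force:
- A reader might take the figure of about half as general. It applies to clinic type at the planned effect with equal groups, or to the four factors jointly. It is about 13% for one evenly split two-level factor and falls quickly if the true effect is larger.
- A reader might think 4.9.2 claims power for differences between subgroups. It does not; its arithmetic concerns arm differences within each subgroup.
- Aim 1 can be read as improvement in every subgroup, not as equal effects. Within-subgroup comparisons then become relevant, but the chance that all three clinic types reach significance is only 0.8³ = 51%, so that reading is not well served either.

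On literacy, 4.9.1 may intend numeracy to stand for the pair, or the word may have been dropped. The text does not settle which. Since two separate instruments are collected, it needs reconciling in either case.

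**Conclusion.** The point holds in a limited form. Aim 1 states a hypothesis about subgroups, section 4.9.1 offers no between-subgroup contrast to address it, and literacy is missing from the list. If consistency were read from separate comparisons, a uniform effect of the planned size would look mixed across three equal clinic types about 48% of the time, with a range of 18% to 74% for true effects 1.25 to 0.75 times the planned one. For each evenly split two-level factor it is about 13%. At the planned effect, clustering or missing data would lower subgroup power and raise these figures.

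It would be going too far to infer that an interaction test settles the hypothesis. At 999 patients the intervals will be wide, and a non-significant result would not prove the effect uniform. The main comparison between arms is unaffected. The change is worth making because it lets the trial address its own stated hypothesis with data it already collects.

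**What to change.** In section 4.9.1:
- Add health literacy to the heterogeneity list, with its cut-point, or state that numeracy is meant to cover both and align the aims.
- For each outcome and each factor (clinic type, cohort, stroke risk, numeracy, literacy), fit one pooled model with arm, factor and arm-by-factor terms, keeping the clinician-level handling already planned.
- Report subgroup effects and the interaction estimate with 95% confidence intervals, for example in a forest plot. State that consistency will not be judged by significance within subgroups.

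In section 4.9.2, clarify that 999 is sized for arm differences within subgroups. Add that an interaction on an evenly split two-level factor has 80% power only at about 6.0 decisional-conflict points or 6.4 knowledge points, so a non-significant interaction does not establish uniformity.

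The cost is some plan wording and a few model terms on variables already collected. The downside is a little more analysis and interaction intervals that will be wide.

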4.9.1.1 Missing Data

We will make every effort to minimize missing data. Trial enrollment and the fidelity of follow-up procedures will be reviewed during bi-weekly conference calls. A study biostatistician will conduct frequency reports to assess for missing data, and the study team, which is experienced in conducting multicenter trials, will trouble shoot any problems encountered. We will report rates of missing data for each outcome by study arm and send missing data reports to sites.

4.9.2 Sample Size Estimation

*The table shows the detectable effect for each of the outcomes of interest if we were to have data on that outcome from a total of 333 patients (1% of available population). This provides enough power ($\alpha=0.05$; two-sided difference) to detect meaningful differences across arms for all SDM quality and process outcomes. Our intent, however, is to have enough power to detect important differences when we conduct analyses of groups or cohorts of patients. Most of these analyses will divide the participants into 2 cohorts (e.g., start and review cohorts), except for the subgroup analysis by clinic, which divides the total sample into 3 cohorts: academic, community, and safety net clinic. That is the only analysis with three groups. Given this, we would need 3 times the sample size listed in the table, or **999 participants (3% of available sample)** to address all planned subgroup analyses. These are minimum targets for recruitment and we do not plan to limit recruitment in any way to enroll up*

to this number of patients. It assumes even distribution of participants per subgroup (e.g., start vs. review cohort); since the only grouping with three levels is clinic, each clinic will be expected to recruit similar numbers. Thus, for the main analysis and for other subgroup analyses (n=2 levels),

Outcome (n = 333)	Rate (%) or SD	Detectable effect	Power*
Patient level – SDM quality			
Knowledge transfer [^]	18	5.6	84%
Knowledge of risk	55%	15%	81%
Decisional conflict scale [^]	17	5.2	80%
Clinician level			
Satisfaction [^]	54%	15%	80%
Encounter level – SDM process			
Engagement (OPTION12) [^]	12.6	3.9	80%

[^] Values from iADAPT SDM tool trial; * $\alpha=0.05$; two-sided

We expect approximately 90% of patients to start (start cohort) or continue a medication (review cohort). Of those, we can reasonably expect to obtain >85% of the pharmaceutical records for those (records will be requested of all enrolled patients regardless of decision). Thus, using the trial size estimated of **999 participants**, we will have ~765 patient records available for assessment of anticoagulant persistence at 12 months (PDC). In our review of the Optum database, 40% of patients were adherent to anticoagulation (>80% PDC, the threshold used by CMS) at 12 months. Assuming an expected rate of 60% PDC for the usual care cohort, we would have 80% power to detect a 9% difference (69% PDC in the SDM tool arm), with a two-sided test and an alpha of 0.05. In subgroup analyses comprising 100 participants per arm and using a one-sided test and alpha of 0.05, we will have 80% power to detect differences of at least 16%.

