4.9.3 Patient Allocation

Eligible patients will be allocated into either the usual care arm or to the usual care + ANTICOAGULATION CHOICE SDM tool (intervention) arm using a random sequence the trial statistician will generate *a priori*. The allocation will be stratified by clinic (academic, community or safety net), by cohort (start or review), and stroke risk (CHA₂DS₂-VASc score of 1 or ≥ 2 for men and 2 or ≥ 3 for women) using blocks of random size.

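### The power table prints 84% for knowledge transfer, but its own inputs (333 patients, SD 18, difference 5.6) give 81%

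*Combined protocol and SAP*

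**What the plan says.** Section 4.9.2 (Sample Size Estimation) introduces its table with "The table shows the detectable effect for each of the outcomes of interest if we were to have data on that outcome", on the condition "if we were to have data on that outcome from a total of 333 patients", with a two-sided alpha of 0.05. The row at issue reads "Knowledge transfer [^] 18 5.6 84" (percent): SD 18, detectable effect 5.6, power 84%. Another continuous row reads "Decisional conflict scale [^] 17 5.2 80" (percent). The remaining rows are OPTION12 (SD 12.6, effect 3.9, power 80%), knowledge of risk (55%, effect 15%, power 81%) and clinician satisfaction (54%, effect 15%, power 80%).

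Section 4.9.1 (Analysis Plan) has "each outcome compared between study arms using t-tests for continuous outcomes". Section 4.9.3 (Patient Allocation) describes two arms but gives no numerical allocation ratio. Section 4.9.2 then triples 333 to 999 so that each of the three clinic types would have the tabulated size.

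**The concern.** All rows share one sample size and one alpha. For the continuous rows, power therefore depends only on the ratio of effect to SD. Knowledge transfer and OPTION12 have practically the same ratio, yet their printed powers differ by 4 points. At least one cell of the knowledge-transfer row (power, SD or difference) must be off.

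SDM quality is the primary endpoint (section 1.0), and knowledge transfer is its first-listed component (section 4.7.1). The table also states the power claimed within each clinic type, since 999 is 3 × 333. There, 84% suggests a margin above 80% that the printed inputs do not provide.

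**Working it through.** **Inputs.** From section 4.9.2: total n = 333, two-sided alpha = 0.05, SD = 18, difference = 5.6, stated power 84%. The t-test comes from section 4.9.1. Equal allocation (166.5 per arm) is assumed, which is the most favourable case for power.

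**Normal approximation.** Power = Φ(δ / (σ√(2/n)) − 1.96), with n per arm.

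- Standard error: 18 × √(2/166.5) = 18 × 0.1096 = 1.973
- Standardized difference: 5.6 / 1.973 = 2.839
- Power: Φ(2.839 − 1.960) = Φ(0.879) = 81.0%

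The noncentral t with 166 and 167 patients gives 80.8%. The plan's 84% is not reproduced.

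**The other rows, same method.** For the two binary rows the power is Φ((δ√n − 1.96√(2p̄(1−p̄))) / √(p₁(1−p₁)+p₂(1−p₂))), taking the effect as an increase from the listed rate.

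| Row | Inputs | Effect/SD | Stated | Normal approximation | Noncentral t |
|---|---|---|---|---|---|
| Knowledge transfer | 5.6, SD 18 | 0.311 | 84% | 81.0% | 80.8% |
| OPTION12 | 3.9, SD 12.6 | 0.310 | 80% | 80.6% | 80.4% |
| Decisional conflict | 5.2, SD 17 | 0.306 | 80% | 79.7% | 79.5% |
| Knowledge of risk | 55% vs 70% | – | 81% | 81.0% | – |
| Clinician satisfaction | 54% vs 69% | – | 80% | 80.6% | – |

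One method accounts for four rows within about 1 point and misses the fifth by 3.

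**Could another convention give 84%?** Each variant below uses the knowledge-transfer inputs and the normal approximation.

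- One-sided alpha 0.05 (the same as two-sided 0.10): 88.4%
- Allocation 1.5:1: 79.4%; 2:1: 76.3%
- Wilcoxon test, relative efficiency 0.955: 79.2%
- Illustrative design effects of 1.05 to 1.2: 79.1% to 73.6%

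None does.

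**What would give 84%?** Changing one input at a time:

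- Sample size: n per arm = 2 × ((1.960 + 0.994) × 18 / 5.6)² ≈ 180.4, so 181 per arm or 362 in total (363 by the t-test)
- Difference: about 5.85 with SD 18 (84.1% by the t-test)
- SD: about 17.2 with difference 5.6 (84.2% by the t-test)

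**The case against.** The best defence is rounding. The SD is printed as a whole number and the difference to one decimal. If the unrounded values were an SD of 17.5 and a difference just under 5.65, power would be 83.6% by the t-test (83.8% by the normal approximation), which prints as 84%. The table marks the SD as coming from an earlier decision-aid trial, so its unrounded value cannot be checked from the documents. This route stays open but is unlikely. It needs both roundings at their favourable extremes at once: rounding the SD alone reaches at most 82.9%, and the difference alone at most 81.5%. The table also prints a decimal SD where it has one (12.6). Even then, the printed inputs would not support the printed power.

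It can also be said that the other rows do not all match to the last digit. Satisfaction computes to 80.6% against 80%, and decisional conflict to 79.5% by the t-test against 80%. The two binary rows would fall to about 78.5% if the effect were a decrease. That is fair, and it is why the agreement is stated as about 1 point. A gap of 3 points still stands out, and the comparison with OPTION12 does not depend on the binary rows.

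Finally, nothing downstream turns on this cell. Three other rows are printed at 80%, so they limit the design at least as much. This is correct and bounds the importance of the point.

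**Conclusion.** The knowledge-transfer power is overstated by about 3 points: 84% printed, 80.8% computed (81.0% by the normal approximation). This assumes equal arms, independent observations and the SD and difference as printed; unequal allocation would lower the figure further. The arithmetic cannot show whether the power, the SD or the difference is the wrong cell, only that the three do not agree.

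The effect on the trial is minor. Power at 333 remains above 80%, the 999 target is unchanged, and at 999 the main comparison of knowledge transfer has about 99.8% power before any allowance for clinician clustering.

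**What to change.** Check which inputs were used for the knowledge-transfer row in section 4.9.2. If SD 18 and difference 5.6 stand, change 84% to 81%. If 84% was the intended power, print a difference of 5.85 with SD 18. If a different SD was used, print it to enough decimals for the row to be reproduced (about 17.2 would be needed with a difference of 5.6). Stating the allocation ratio beside the table would remove the one assumption a reader now has to make.

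The cost is one corrected table row and a slightly less favourable stated power. Recruitment, analysis and the 999 target are unaffected.

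### Persistence is sized on, and by the PDC definition computable only in, patients who take up an anticoagulant after randomisation, so the comparison as written is not protected by randomisation

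*Combined protocol and SAP*

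**What the plan says.** Aim 2 (section 1.0) describes the tool's impact on anticoagulation rate, choice of agent and adherence. It asks for "12-month drug persistence, in all patients and in subgroups defined by patient literacy/numeracy, stroke risk, anticoagulation use at baseline, and type of clinic". Section 4.9.1 states an intention-to-treat analysis, "including all patients enrolled to the study in the arm to which they were assigned", with imputation for missing values.

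Section 4.9.2 builds the persistence sample in two steps from "999 participants". The first is "We expect approximately 90% of patients to start (start cohort) or continue a medication (review cohort"). The second is "Of those, we can reasonably expect to obtain >85% of the pharmaceutical records for those". The result is that "we will have ~765 patient records available for assessment of anticoagulant persistence at 12 months (PDC"). The same passage adds that "records will be requested of all enrolled patients regardless of decision".

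Section 4.7.3 defines PDC as days supplied divided by days observed, with observation starting at the first fill. It gives no rule for a patient with no fill. The same section lists the rate of anticoagulation as a separate outcome. Under 4.5 the clinician is told before entering a standard-care encounter that the tool is not to be used, so the arm is settled before the treatment decision is made.

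**The concern.** Whether a patient starts, continues or declines is decided in or after the randomised encounter, and changing that decision is part of what the tool may do. A persistence comparison confined to patients who fill a prescription therefore compares groups that the intervention may have helped to form. If the tool brings in hesitant patients who later lapse, persistence among users falls in the tool arm even though more patients are covered. If it leads hesitant patients to decline, persistence among users rises although nobody extra is treated. Either result could be reported as an adherence effect when it reflects only who took up treatment.

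The intention-to-treat and imputation sentence does not settle this. For a patient who never fills, PDC as defined has no starting date: it is undefined rather than missing. Imputing it from users would credit treatment coverage to people who took none. Section 4.9.1.1 on missing data names no imputation method and does not address the case.

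**Working it through.** **Inputs from the plan (4.9.2).** Total 999; 90% start or continue; 85% of those with pharmacy records; usual care 60%, tool arm 69%; two-sided alpha 0.05. The 60% and 69% are read as proportions of adherent patients, since no standard deviation is given for a mean PDC. Allocation of 1:1 is assumed, because 4.9.3 gives no ratio.

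**Step 1: the plan's record count.** 999 × 0.90 = 899.1, and 899.1 × 0.85 = 764.2, which matches about 765. Without the 90% factor the count is 999 × 0.85 = 849.2. The 10% are thus left out because of their treatment decision, although records are requested from everyone.

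**Step 2: what PDC can be computed for.** The denominator in 4.7.3 runs from the first fill. A patient with no fill has neither a denominator nor an assigned value, so the calculation drops that patient whatever the 90% was meant to do.

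**Step 3: effect of selection (assumed uptake and adherence).** Let uptake be u0 in usual care and u1 in the tool arm, with u1 > u0. Suppose the tool changes uptake only, patients who would take the drug in either arm are 60% adherent, and the extra takers are 30% adherent.

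- Adherent among users, tool arm: (0.60·u0 + 0.30·(u1 − u0)) / u1. Usual care: 0.60.
- Adherent among all patients, non-users scored not adherent: tool arm 0.60·u0 + 0.30·(u1 − u0); usual care 0.60·u0.

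| Uptake, usual care v tool | Users, tool arm | Difference among users | Difference among all patients |
|---|---|---|---|
| 88% v 92% | (0.528 + 0.012)/0.92 = 58.7% | −1.3 points | 54.0% − 52.8% = +1.2 points |
| 85% v 95% | (0.510 + 0.030)/0.95 = 56.8% | −3.2 points | 54.0% − 51.0% = +3.0 points |

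The two comparisons can differ in sign. The distortion is small when uptake differs little.

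**Step 4: size and power of an all-patient comparison.** With 90% uptake in both arms and non-users scored not adherent, 60% v 69% becomes 0.90 × 0.60 = 54.0% v 0.90 × 0.69 = 62.1%, a difference of 8.1 points. A two-proportion z-test (pooled variance under the null) gives:

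| Comparison | Records | Rates | Power | Detectable at 80% power |
|---|---|---|---|---|
| Users only | 765 (382.5 per arm) | 60% v 69% | 74% | 9.7 points |
| All with records | 849 (about 425 per arm) | 54% v 62.1% | 67% | 9.5 points |

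The users-only figure is 74%, not the 80% stated in 4.9.2. That is a separate matter, but it is the right benchmark for the cost of the fix.

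**The case against.** The strongest reply is that 4.9.2 is a forecast of available records, not a definition of an analysis set. A reader might infer that the plan formally limits persistence to the 90%, but the documents do not say so. Section 4.9.1 analyses everyone as assigned, records are sought from everyone, and the only stated exclusion from the adherence analysis is a patient who declines the records authorization (4.2.3). This stands. The point is therefore that the sizing and the PDC formula together produce a restricted set that the intention-to-treat statement contradicts.

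Other parts of the reply also stand:

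- In Aim 2, the reference to all patients is paired with subgroups. It may mean only the overall sample, so it does not by itself prove that non-users were to be included.
- A patient who declines at the encounter is not necessarily uncovered. Section 4.7.3 recognises that decisions may be confirmed after the visit, and a later fill is possible. Coverage has to be read from fills, not from the stated decision.
- Uptake is reported as its own outcome, so a shift would be visible beside persistence. In a shared-decision trial, declining can be a legitimate choice, and persistence among users is a reasonable descriptive question. It is still not a randomised comparison.
- A reader might infer that a large false-positive finding is likely. One can construct such a case: usual-care uptake 90%, tool-arm uptake 80%, and marginal patients never adherent give 54% adherent overall in both arms but 0.54/0.80 = 67.5% v 60% among users, significant about 58% of the time at 382 per arm. Nothing in the documents supports so large a shift. Equal arms also ignore the smaller tool-arm group it implies (499.5 × 0.80 × 0.85 = 340). It shows a limit, not an expectation.

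**Conclusion.** The concern holds in this form: persistence is sized on patients who take up treatment and, by the PDC definition, can be computed only in patients who fill, while 4.9.1 promises all enrolled patients as assigned. The comparison that results conditions on a post-randomisation event the tool may change. The documents do not establish that a restricted set was deliberately chosen; they leave the population and the value for a never-filler unspecified.

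The size of any bias cannot be fixed from the documents, because they give no uptake by arm and no adherence for marginal patients. Under the assumptions shown it is about 1 point at 88% v 92% uptake, and about 3 points with a reversal of sign at 85% v 95%, against a 9-point target difference. Persistence is not the primary endpoint and the remedy uses data already to be requested, so this is a worthwhile, low-cost improvement rather than a threat to the trial's main result.

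**What to change.** In 4.7.3, 4.9.1 and 4.9.2:

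1. Add, as the randomised persistence comparison, all randomised patients with pharmacy records, by assigned arm. Count days covered from the index encounter, and score patients with no fills as 0 (not adherent). State how supply already in hand at the encounter is counted; the 12 months of earlier fills to be requested allow this.
2. Keep PDC among patients who start or continue as a secondary result. Label it as conditional on a choice made after randomisation, and show it beside uptake by arm.
3. Restate the size as about 849 records. This assumes that the 85% retrieval rate, which 4.9.2 gives only for patients who start or continue, also applies to non-users.

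The cost is wording and a less favourable power statement: about 67% for 54% v 62.1% with equal 90% uptake (detectable difference about 9.5 points), against about 74% for 60% v 69% in the conditional comparison at about 765 records. No new data collection is needed.
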